6.3.4. Definition of enrollment

A subject is considered enrolled in the clinical investigation after they have provided written informed consent, and if they meet the preoperative eligibility criteria (Section 6.3.1 and Section 6.3.2). The study will treat up to 73 subjects with the investigational device. Treated subjects include subjects that are actually implanted with the device, or had a treatment attempt with the device.

6.3.5. Randomization

N/A. This is a non-randomized clinical investigation.

6.3.6. Sample size

The current plan is to treat a total of up to 51 subjects with GATT-Patch, with a maximum of 153 replaceable subjects that may be enrolled (Section 6.3.9). However, the total sample size may increase to a maximum of 73 treated subjects based on the interim sample size re-estimation. The sample size calculation is provided in Section 7.2. It is expected that a comparable number of subjects is enrolled and treated at each investigational site.

In Stage I, there is a minimum of 2 subjects to be treated by each site (maximum of 3 sites). In Stage II, there is no minimum or maximum number of subjects to be enrolled or treated by each site, however distribution between participating sites is monitored during the enrolment period.

6.3.7. Study duration

The enrollment period is expected to take approximately 6 months. The per subject duration of the clinical investigation from treatment to final follow-up will be approximately 6 weeks. With a 2-week temporary hold on enrollment for the safety evaluation, the total expected duration of the clinical investigation is, therefore, approximately 8 months. GATT-Patch is expected to resorb within 4-6 weeks, and 6 weeks follow-up is therefore considered sufficient for the assessment of performance and safety of the device.

6.3.8. Subject withdrawal, discontinuation and study end

A subject may withdraw or discontinue participation at any time during the clinical investigation. There is no need to provide a reason for withdrawal or discontinuation. The investigator may also decide to stop a subject's participation in the clinical investigation, for example due to non-compliance to the clinical investigation plan or if the investigator feels it is in the subject's best interest to stop.

The Sponsor or its representative will be notified immediately when a subject is withdrawn or discontinued for any reason. Premature clinical investigation end date and reason (if known) will be documented on the case report forms. If a subject fails to return for the follow-up visit, the investigator will attempt to contact the subject to determine and document the reason for the subject failed to return and to encourage compliance with the study visit schedule. The investigator will ask for the subject's permission to follow his/her status/condition outside the study.

The data collected up to the time point the subject has withdrawn or discontinued will be included as part of the clinical investigation results. Additional safety information may be requested from a withdrawn or discontinued subject if it is considered clinically relevant. Subjects who withdrawn from the study will receive standard of care defined by applicable treatment protocol(s) for the disease at the investigational site. If any additional care is necessary because of the subjects' participation in the clinical investigation, this will be provided to the subject by the investigational site.

6.3.9. Subject replacement

The current plan is to treat a total of 51 subjects with the investigational device. However, the total sample size may increase to a maximum of 73 treated subjects based on the interim sample size reestimation. There will be no replacement of subjects who have been treated with the investigational device. Intraoperative eligibility after informed consent is estimated at 50%, where the other 50% of patients will have no bleeding requiring device use. In case this 50% is an underestimate of intraoperative inclusion, there is a limitation of replacement that is set at 153 patients, representing

Page 34 of 62

a rate of 25% of patients being able to be included intraoperatively. A re-evaluation of inclusion and exclusion criteria will be performed when a total of 51 treated subjects is not reached when the maximum of 153 subjects are replaced.

6.3.10. Investigational sites

This clinical investigation will be conducted in the Netherlands. Up to 7 sites will participate in this clinical investigation, with a maximum of 3 sites in Stage I. Any differences between site environment will be minimized through central training of the investigators and adherence to the same clinical investigation plan. Each site has a clinical environment that is representative of the normal conditions of use of the device in the target population.

Contact and site details of each participating site are listed in a separate document. Emergency contact details are provided the contact information sheet on page 4.

6.4. Procedures

GATT-Patch will be used to control bleeding during open liver surgery. Each surgery will be performed according to the standard procedures of the hospital, with exception of the use of GATT-Patch. GATT-Patch will be used if the subject has an appropriate bleeding site (SBSS 1, 2 or 3 and no contraindications).

6.4.1. Schedule of assessments

Table 4 provides a schedule of assessment for subjects screened and enrolled in the clinical investigation. All assessments are applicable for treated subjects, while only the assessments related to 'screening' and 'admission' are applicable for subjects that are enrolled but not treated.

Assessments	Screening	Admission before surgery	Treatment with	Hospitalization after surgery	Week 6 (±2 weeks)
			investigational		Post-
			device		procedure*
Informed consent	Х				
Inclusion and	Х	Х	Х		
Exclusion Criteria					
Baseline	Х				
demographics					
Physical examination	Х	Х			
Relevant	Х	Х			Х
concomitant					
medication**					
Medical	Х				
history/Allergy					
Laboratory tests	Х	Х		Х	
Procedural data			Х		
Adverse events			Х	Х	Х
User questionnaire			Х		
Ultrasound imaging					X

TABLE 4: SCHEDULE OF ASSESSMENTS

* Some subjects may have an additional phone consultation at 2-6 weeks post-procedure for the assessment of safety during Stage I of the clinical investigation. This visit will include assessment of adverse events, and will only take place for subjects in stage I of the clinical investigation who did not complete the 6 weeks follow-up visit.

DHF-01-QR-021 Confidential Page 35 of 62

** Relevant concomitant medication will be captured from screening to study completion. Medication is considered relevant when related to any of the study eligibility criteria, or when it may affect any of the endpoints, at the discretion of the investigator. Relevant medication covers at a minimum the medication for the underlying medical condition for the surgical procedure, and medication for concomitant chronic pathologies.

6.4.1.1. Laboratory Tests

Laboratory tests will be collected prior to surgery, and through the postsurgical admission. The collection of laboratory tests is specified in Table 5. Tests that are indicated with an 'X' are required per this clinical investigation plan. Tests that are indicated with an '*' are not dictated by this clinical investigation plan: results will only be captured if these test data is collected per standard of care.

Laboratory Tests	Screening	Admission before	Through
		surgery	aumission
Hematology			
Hemoglobin (Hb)	Х	*	Х
Thrombocytes	Х	*	*
Coagulation			
Prothrombin time (PT)	Х	*	*
Activated partial thromboplastin time (aPTT)	Х	*	*
International Normalized Ratio (INR)	Х	*	*
Chemistry			
Bilirubin	Х	*	*
Calcium	*	*	*
Potassium	*	*	*
Sodium	*	*	*
Chloride	*	*	*
Albumin	*	*	*
AST	*	*	*
ALT	*	*	*

TABLE 5: LABORATORY TESTING SCHEDULE

* Timing of collection if this data will be according to standard of care hospital procedures.

6.4.2. Equipment for assessment

The following equipment will be required for assessment of endpoints:

- Ultrasound imaging system
- Stopwatch

6.4.3. Screening

During the Screening phase, the following assessments will be performed:

Informed consent

If the patient meets the criteria of the initial screening, informed consent will be obtained. Before performing any study-specific procedures, the potential subject must be thoroughly informed about all aspects of the clinical investigation, including scheduled study visits and activities, and must have signed the Ethics Committee-approved informed consent form. See also Section 12 for more details.

DHF-01-QR-021 Confidential Page 36 of 62

Baseline data

The following baseline demographics will be captured, if available:

- **Demographics:** Subject demographics (age, gender, race) will be recorded.
- Physical examination
- Relevant concomitant medication
- **Medical history:** The subject's relevant medical history will be recorded. Medical history is considered relevant when it is currently ongoing, when it is related to any of the study eligibility criteria, or when it may affect any of the endpoints. Relevant medical history covers at a minimum the underlying medical condition for the surgical procedure.
- Laboratory test data

6.4.4. Admission before surgery

The following baseline data will be captured during admission before surgery:

- Confirmation of inclusion/exclusion criteria
- Physical examination
- Relevant concomitant medication
- Laboratory test data

6.4.5. Treatment

GATT-Patch will be used to control bleeding during open liver surgery. Each surgery will be performed according to the standard procedures at the hospital, with exception of the use of GATT-Patch. GATT-Patch will be used if the subject has an appropriate bleeding site (SBSS 1, 2 or 3 and no contraindications). Use of GATT-Patch will only be considered during and/or after resection when control of bleeding by standard surgical techniques (such as suture, ligature or cautery) is ineffective or impractical, and the surgeon has made the decision to apply a topical hemostatic product. If there are multiple appropriate bleeding sites, the first encountered bleeding site that requires topical hemostat application will be considered for the primary endpoint.

The handling instructions for GATT-Patch are provided in the Instructions for Use of the device (DHF-01-QR-008). Select the appropriate size of the patch so that it overlaps the margins of the bleeding surface by at least 1 cm. The patch may be cut to the desired size and shape. Dry gloves and surgical instruments (forceps, scissors) should be used to handle, cut and apply GATT-Patch. GATT-Patch can be placed on a wet gauze prior to placement, and after excess blood is removed from the bleeding site, directly applied on the bleeding site with continuous pressure. Failure is considered if after 5 minutes no hemostasis was obtained. Up to 3 full patches may be used. The patch may be applied to or overlap a previously applied patch ("patch on patch").

Achievement of hemostasis will be verified every 30 seconds. The primary performance endpoint is defined by the percentage of cases achieving hemostasis at 3 minutes. Hemostasis will be defined by a grade of 0 (None/Dry) on the SBSS¹⁰. If hemostasis has not been achieved after 5 minutes of

¹⁰ The Surface Bleeding Severity Score (SBSS) provides a validated score for assessment of bleeding at the target site, and consists of 6 subscales (0=none, 1=minimal, 2=mild, 3=moderate, 4=severe; not immediately life-

application (SBSS 1-5), then treatment is considered a failure and other additional hemostatic agents/techniques may be used. This should not be GATT-Patch. In the case 3 full GATT-Patches have been applied and a bleeding site other than a previously treated target bleeding site is identified, other additional hemostatic agents/techniques may be used.

The investigators will complete a user questionnaire at the end of each procedure. During surgery, photos and videos may be taken for documentation and/or training purposes. Patients will not be recognizable in these photos and videos.

The following procedural data will be collected:

- Surgical procedure data:
 - Date of surgery (month/year)
 - Procedure length (from start incision to surgical site closure)
 - o Number of devices used
 - Blood loss (mL)
 - SBSS (0-5) of target bleeding site
 - Use of adjunct hemostatic agents/techniques (e.g., cautery, sutures or staples)
 - o Amount of material needed versus bleeding surfaces
 - o User satisfaction per investigator per procedure (questionnaire)
- Hospitalization:
 - \circ $\;$ Duration of patient's time spent in the intensive care unit
 - o Total hospitalization period
 - o Blood transfusion (mL)
- Intraoperative device and/or procedure related adverse events
- Intraoperative device deficiencies

6.4.6. Hospitalization after surgery

The following data will be captured the during hospitalization after surgery:

- Laboratory test data
- Intraoperative device and/or procedure related adverse events

6.4.7. Visit 1 (Week 6)

At follow-up Week 6 (±2 weeks), subjects will undergo ultrasound examination of the resection area to identify any encapsulation or rolled-up device, or evidence of a biloma or pseudo-aneurysm. In addition, relevant concomitant medications and adverse events will be assessed.

Optional: Some subjects may have an additional phone consultation at 2-6 weeks post-procedure for the assessment of safety during Stage I of the clinical investigation. This visit will include assessment of adverse events, and will only take place for subjects in stage I of the clinical investigation who did not yet complete the 6 weeks follow-up visit.

threatening, 5=extreme; immediately life threatening) (Spotniz, 2017). Investigators will be trained on the assessment scale prior to the investigation to have consistent assessment of bleeding at the target site.

6.4.8. Study completion

The study is completed when the 51 subjects were treated with the investigational device or when the number of subjects needed based on the planned interim analysis of the primary performance endpoint is treated with the investigational device, and the last treated subject completed the follow-up Visit 1, is lost to follow-up or pre-maturely ended the study for some other reason. Subjects are lost to follow-up when the following steps have been taken:

- Two phone calls should be made to the subject. Each attempt should be clearly documented in the source documents and the response or lack thereof should be captured.
- If there is no response to the phone calls, then certified letter should be written to the subject. A copy of the letter should be retained in the subject's source document.
- After a period of two (2) weeks following completion of the above actions, the subject will be considered Lost to Follow-up. The sponsor should be notified and appropriate eCRF should be completed.

6.4.9. Activities by Sponsor representatives

Procedures related to the clinical investigation will be performed by the principal investigator, study coordinators, and/or other authorized study staff, as applicable. A Sponsor representative may be present during investigational procedures for technical support. Photos and videos may be taken by the Sponsor representative for documentation and/or training purposes. Patients will not be recognizable in these photos and videos.

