13.1.1. Adverse events

An adverse event is any untoward medical occurrence, unintended disease or injury, or untoward clinical signs (including abnormal laboratory findings) in subjects, users or other persons, whether or not related to the investigational medical device and whether anticipated or unanticipated.

This definition includes events related to the investigational medical device; events related to the procedures involved. For users or other persons, this definition is restricted to events related to investigational medical devices.

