The Sponsor and the investigators will distinguish between the serious adverse events related to the investigational device and those related to the procedures (any procedure specific to the clinical investigation). An adverse event can be related both to procedures and the investigational device. Complications caused by concomitant treatments not imposed by the clinical investigation plan are considered not related. Similarly, several routine diagnostic or patient management procedures are

¹⁴ If an investigational device gives an incorrect diagnosis, the patient might, for example, receive an unnecessary treatment and incur all the risks that accompany that treatment, or might be incorrectly diagnosed with a serious disease. In other cases, the patient might not receive an effective treatment (thereby missing out on the benefits that treatment would confer), or might not be diagnosed with the correct disease or condition.

applied to patients regardless of the clinical investigation plan. If routine procedures are not imposed by the clinical investigation plan, complications caused by them are also considered not related.

In some particular cases the event may be not adequately assessed because information is insufficient or contradictory and/or the data cannot be verified or supplemented. The Sponsor and the investigators will make the maximum effort to define and categorize the event and avoid these situations. Where an investigator assessment is not available and/or the Sponsor remains uncertain about classifying the serious adverse event, the Sponsor should not exclude the relatedness; the event should be classified as "possible" and the reporting should not be delayed.

Particular attention will be given to the causality evaluation of unanticipated serious adverse events. The occurrence of unanticipated events related to the use of the device could suggest that the clinical investigation places subjects at increased risk of harm than was to be expected beforehand.

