13.5. Non-reportable adverse events

N/A. This is a pre-market clinical investigation and all procedure- and device-related AEs will be reported for this clinical investigation.

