13.6. Reporting requirements

13.6.1. Reporting adverse events

Adverse event reporting will start at the time of surgery and ends after the last subject completed the clinical investigation. Adverse events that occur between the signing of the informed consent and the initiation of the surgery will thus not be reported on the eCRFs. Underlying diseases are not reported as adverse events, but any deterioration in severity will be reported.

Adverse event information will be collected for all subjects. At every subject visit, the investigator will determine whether an adverse event has occurred since the last visit. All adverse events will be reported in the eCRF. The date of the initial event and the subsequent treatment will be documented.

Adverse events will be evaluated and differentiated by:

- Seriousness of the event
- Causality of the event (in relation to the device or procedure)
- Severity of the event

13.6.2. Reporting device deficiencies

All device deficiencies related to the identity, quality, durability, reliability, safety or performance of an investigational medical device will be documented throughout the clinical investigation and appropriately managed by the Sponsor.

13.6.3. Reporting serious adverse events and serious adverse device effects

Reporting requirements to the Sponsor and Regulatory authorities are summarized in the sections below.

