10 SAFETY ANALYSES

Safety analyses will be performed for the Safety population and will be descriptive and narrative in nature, including definitions of severity and relation for all adverse events, and focusing on serious adverse events.

The number and percent of patients with any adverse event, any serious adverse event, any adverse event related to the study device, and any adverse event related to study procedure will be presented. Summaries will be presented by study stage and overall.

No formal hypothesis testing will be performed.

11 Adverse Events

All adverse events (AEs) collected between the index procedure and the 6 weeks (+/-2 weeks) follow-up visit will be recorded in the eCRFs and will be reported. All adverse events (AEs) will be coded using the standardized Medical Dictionary for Regulatory Activities (MedDRA) central coding dictionary, version 24.0 or later. The analysis is performed on the safety population.

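### The protocol gives conflicting scopes for adverse-event capture: the hospital-stay list names only intraoperative related events, while the reporting section and the planned tables need all events.

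*Protocol*

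**What the plan says.** The protocol describes the scope of adverse-event capture in several places.

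- **6.4.5 (Treatment) and 6.4.6 (Hospitalization after surgery)** carry the same item: "Intraoperative device and/or procedure related adverse events". In 6.4.6 it is the only adverse-event item.
- **13.5 (Non-reportable adverse events)** is marked not applicable and then says that "all procedure- and device-related AEs will be reported for this clinical investigation".
- **13.6.1 (Reporting adverse events)** says "All adverse events will be reported in the eCRF". It sets the window ("Adverse event reporting will start at the time of surgery and ends after the last subject completed the clinical investigation") and the enquiry ("At every subject visit, the investigator will determine whether an adverse event has occurred since the last visit").
- **13.1.1** defines an adverse event as an untoward occurrence "whether or not related to the investigational medical device and whether anticipated or unanticipated".
- **Table 4** marks adverse events at treatment, at hospitalization after surgery and at Week 6, with no limit by relatedness or by time of onset.

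On the analysis side, SAP section 10 will present "The number and percent of patients with any adverse event, any serious adverse event", with device-related and procedure-related events as further rows. Protocol 7.1.3 plans the same. SAP 11.1 tabulates all events by severity and by relationship to the investigational product.

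On classification, protocol 4.3 describes complications of open liver surgery as procedure-related. Section 13.2 says: "If routine procedures are not imposed by the clinical investigation plan, complications caused by them are also considered not related".

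**The concern.** Site staff work from visit lists. The list for the postoperative stay asks for a kind of event that cannot begin during that stay, and only if it is already judged related. Section 13.5 can be read as keeping the relatedness limit. The planned tables need every event, related or not.

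The safety endpoint is the incidence of device-related events, compared descriptively with the literature, and the SAP makes an acceptable safety assessment a condition of study success. If some sites follow the visit list and others follow 13.6.1, event counts would differ for reasons unrelated to the device, and the error would be towards under-recording. Where relatedness decides whether a non-serious event is entered, that judgement cannot be revisited from the database.

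**Working it through.** The plan states no figure on this point, so the main check is to set the texts side by side.

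| Place | Limited to events during surgery? | Limited to related events? |
|---|---|---|
| 6.4.5, 6.4.6 | Yes | Yes |
| 13.5 | No | Yes, on its wording |
| 13.6.1 with 13.1.1 | No | No |
| Table 4 | No | No |
| 6.4.7 (Week 6) | No | No |
| Analyses: protocol 7.1.3, SAP 10 and 11 | No | No |

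There are three scopes, and only the broadest supports the planned tables. No section ranks one above another. The conflict lies inside the protocol as well as between protocol and SAP, because 7.1.3 also counts events of any kind.

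**What a literal reader of 6.4.6 would miss.** Any event starting on the ward falls outside the item, including a device-related one. The next scheduled assessment without restriction is Week 6 ± 2 weeks: 6 − 2 = 4 to 6 + 2 = 8 weeks after surgery. The optional phone contact at 2 to 6 weeks is for Stage I subjects only, so a Stage II subject has nothing scheduled in between.

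**What is protected.** Under 13.6.3.1 investigators notify all serious events within 24 hours. Section 13.6.3.2 requires them to be reported whether or not device-related, and 13.8 refers them to the DMC. Section 13.1.2 counts prolonged hospitalization, and intervention to prevent life-threatening illness or permanent impairment, as serious. What remains exposed is mainly non-serious events.

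**Size per missed subject.** SAP 5.1.1 gives 8 treated in Stage I. SAP section 4 gives 39 planned in Stage II, and at most 61 after re-estimation.

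- Planned: 8 + 39 = 47; 1/47 = 2.1 percentage points.
- Maximum: 8 + 61 = 69; 1/69 = 1.4 percentage points.

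Protocol 3.2 gives 0-6.7% for device-related events with benchmark devices, leaving aside one report of 18.2%. The upper end corresponds to 0.067 × 47 = 3.1 subjects, so one or two missed subjects would be visible in that comparison. This applies only to missed device-related events. The documents give no basis for estimating how many would be missed.

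**The case against.** The strongest reply is that the operative text is clear. Section 13.6.1 is the reporting section, it requires all events, and it requires an enquiry at every visit about the time since the last one. Table 4 marks the hospital stay without restriction, so the 6.4.6 item looks like a bullet copied from 6.4.5. Section 13.5 sits under a heading marked not applicable and may mean only that nothing is exempt: it says all related events are reported, not that only these are. The eCRF is not among the documents and may already use the broad scope. All of this stands. It limits the consequence but leaves the conflicting wording in place.

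Four stronger readings are tempting, and the documents do not support them.

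- A reader might infer from 13.5 and 13.2 together that ordinary postoperative complications go unreported. Section 13.2 governs how events are classified, not whether they are captured, and its scale has a not-related level. Causality under 13.6.1 and the relationship tables in SAP 11.1 presuppose that unrelated events are in the database.
- A reader might infer that serious-event rates would vary by site or escape the DMC and medical monitor. The mandatory route for serious events answers that.
- A reader might infer that the denominators would differ by site. They are treated subjects; only event counts could differ.
- A reader might infer that every missed event distorts the comparison with the literature range. That range covers device-related events, so a missed unrelated event cannot move it. Encapsulated device and biloma are also looked for by ultrasound at Week 6, so they depend less on the ward list than rebleeding, infection or thromboembolic events do.

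**Conclusion.** The concern holds as an inconsistency with a limited but real consequence. The 6.4.6 item does not fit the visit it describes, and 13.5 is worded more narrowly than 13.6.1. The exposure is mainly non-serious postoperative events during admission, including device-related ones if 6.4.6 is followed literally, together with non-serious unrelated events. They may be recorded late, from recall at Week 6, or differently between sites. This assumes that at least one site works from the visit list and that the eCRF does not correct it; neither can be checked here. The 2.1 and 1.4 points are the effect of one missed device-related subject, not a forecast of bias. Sample size, alpha and power are unaffected.

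A secondary point concerns classification. Section 4.3 treats complications of open liver surgery as procedure-related. Section 13.2 takes procedures to be those specific to the investigation and treats complications of routine procedures as not related. The note in 4.2 sends adjudication to the Section 13 definitions, which answers part of this, but the SAP does not say in which class complications of the resection itself are counted.

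**What to change.** 1. In 6.4.5, 6.4.6 and 13.5, replace the restricted wording with all adverse events, regardless of relationship, to match 13.6.1, Table 4 and SAP sections 10 and 11.
2. Remove the word intraoperative from the 6.4.6 item, so that it covers events arising during the stay.
3. Confirm that the eCRF adverse-event form and its completion instructions use the same scope. If they used the narrow one, check hospital stays already completed, including Stage I, against source records.
4. State in 13.2 and in the SAP whether complications of the liver resection itself count as procedure-related, and use that definition in 4.3 as well.

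The cost is protocol and SAP wording, plus some extra event entry at any site that had used the narrow reading.
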